2.0 Introduction

2.1 Background and Rationale

Motor Neurone Disease (MND) is known to affect the motor system and other circuitry in the central nervous system. It is well established that up to 15% of people with MND can develop Frontotemporal Dementia (FTD), displaying complex changes in ‘personality’/behaviour and cognitive functioning (i.e. planning, concentration and language ability). There is evidence that MND patients can also present with non-motor symptoms, which are defined as cognitive and behavioural changes or impairments, even without full-blown MND-FTD (MND combined with FTD). Furthermore, the National Institute for Health and Care Excellence (NICE) MND guidelines published in February 2016, place an emphasis on the importance of non-motor cognitive and behavioural symptom assessment in the scope of disease management (NICE, 2016a). This is further supplemented with new publication of diagnostic guidelines for MND-FTD, with a stronger emphasis on detection of cognitive and behavioural symptoms that could occur in up to 50% of MND patients (Strong et al., 2017), known as MND with cognitive impairment and/or behavioural impairment.

There are multiple, quick and effective screening methods available for cognitive and behavioural impairment in MND, which have been noted in a systematic review of literature (Simon & Goldstein, In Press). These include the Edinburgh Cognitive and behavioural ALS Screen (ECAS; Abrahams et al., 2014), ALS Cognitive Behavioral Screen (ALSCBS; Woolley et al., 2010), Mini-Addenbrooke’s Cognitive Examination (Mini-ACE; Hsieh et al., 2015) and Motor Neuron Disease Behavioural Instrument (MiND-B; [name] et al., 2014). With these tools, there is increased awareness, more routine assessment and improved detection of cognitive and behaviour changes in MND for healthcare professionals (HCPs). A recent systematic review showed that behavioural impairment (such as lack of motivation or impulsivity) were associated with increased burden (de Wit et al., 2018). Earlier research has shown that behaviour, as well as cognitive impairment, impacts burden in family members (e.g. Burke et al., 2015; Watermeyer et al. 2015). In dementia, impairments relating to cognition or behaviour are manageable through codes of practice applicable to specialist clinics and community teams (NICE, 2016b). Therefore, it is timely to explore tools that might help manage these impairments for both families and HCPs in MND.

The MiNDToolkit was created for management of behavioural impairment in MND. This Toolkit was comprehensively created through surveying research literature and multiple consultations with allied HCPs (e.g. Occupational Therapists, Speech and Language Therapists, Specialist Nurses), internationally expert clinicians, international expert researchers, family members of people living with MND-FTD and also people living with MND.

For carers, the MiNDToolkit comprises several psychoeducational online modules that are tailored for the symptoms they are dealing with. For HCPs, the MiNDToolkit is a composition of tools inclusive of educational information, structured interactive clinical reasoning and techniques for management of behavioural change of people with such impairments or MND-FTD.

2.2 Trial Objectives

Before conducting a large-scale randomized controlled trial of the MiNDToolkit as an intervention, it is important to answer the question “Can this study be done?” (NIHR, 2019). Therefore, there is need for a feasibility study to inform the design of future trials.

This feasibility study aims:

- 1) To test the feasibility of the MiNDToolkit online intervention in MND Specialist Settings;
- 2) To explore the potential of several outcome measures for future evaluation studies (trials).

3.0 Study Methods

3.1 Trial Design

This study is a pilot, small-scale, open-label, randomised controlled trial to determine the feasibility of the MiNDToolkit for use by carers (family carer/relative/live-in professional carers) with optional support from HCPs.

3.2 Allocation

After completion of pre-intervention assessments, eligible participants will be randomized by the Norwich CTU, using a randomisation table provided by the study statistician. Participants will be allocated to either the MiNDToolkit intervention group or usual care group, the control group. The platform will automatically notify MiNDToolkit-trained HCPs at sites of participants assigned to the MiNDToolkit intervention group.

3.3 Sample Size

The sample size is not based upon any statistical considerations but upon practical considerations and typical sample sizes for feasibility studies. The MiNDToolkit intervention will involve up to 30 carers (family carer/relative/live-in professional carer) of people with MND, with additional behavioural impairments. This requires 2 to 3 participants per site.

3.4 Interim analyses and stopping guidance

No formal interim analyses or stopping rules based upon efficacy are planned.

3.5 Timing of outcome assessments

Assessments will be made at baseline prior to randomization and post intervention (within one month of the end of the intervention period of 3 months).

4.0 Statistical Principles

4.1 Treatment Adherence

No definition of treatment adherence is provided and no definition is required to define any analysis population. Assessing adherence is an objective of the study.

4.2 Protocol deviations

All major deviations from protocol will be recorded and should be reported as part of the study output. These may inform the design of a future trial.

4.3 Analysis populations

All participants randomised to the study will represent the study population for analyses related to efficacy outcomes and follow-up, excluding any participants who withdraw and do not provide or agree to use of relevant data. An Intention-to-Treat (ITT) approach will be used when making group comparisons as an estimate of intervention effect.

5.0 Trial Population

Potential participants are carers of people with MND with additional behavioural symptoms. For more details see eligibility section below. Participants are identified nationally. The intention is to secure 10 sites across England and Wales.

5.1 Screening data

Participants complete the screening and baseline assessment questionnaires online. Some measures (e.g. ALSFRS-R adapted) are modified in terms of sentence construction, as they are being completed by the carer.

This assessment will include the Motor Neuron Disease Behavioural Instrument (MiND-B; [name] et al., 2014).

Additional information to characterize the screened group includes:

- Carer socio-demographic details.
- ALS-Functional Rating Scale Revised (ALSFRS-R; Cedarbaum et al., 1999), adapted for completion by carer.

5.2 Eligibility

Eligibility to the study is decided based upon the following entry criteria.

5.2.1 Inclusion Criteria:

1) Participants are family carers, relatives or live-in professional carers of:

- Patients with a diagnosis of MND with cognitive impairment or behavioural impairment, based on Strong et al. (2017) diagnostic criteria, or
- Patients with a diagnosis of MND-FTD based on Strong et al. (2017) diagnostic criteria.

2) Carers will have at least 7 hours of contact with the person with MND per week and be willing to participate in research activities.

3) Carers must be aged 18 years or over.

5.2.2 Exclusion Criteria:

1) Inability to read or communicate in English (with or without support).

2) Participant is a carer of a patient who already has a carer recruited into the study.

5.3 Recruitment and participant flow

Figure 1 indicates the pre-trial planned participant flow.

[figure not shown]

Figure 1: Participant Flow

5.5 Baseline participant characteristics

The characteristics of all participants at baseline will be compared between treatment group. No formal hypothesis testing will be carried out.

The following characteristics will be summarised using descriptive statistics:

- Demographic details.
- Person with MND clinical phenotype.
- Information regarding care provided by the carer.
- The Patient Health Questionnaire 9 (PHQ-9; Kroenke et al., 2003) for the carer.
- The Generalized Anxiety Disorder Questionnaire 7 (GAD-7; Kroenke et al., 2007) for the carer.
- The Carer Experience Scale (CES; Al-Janabi et al., 2008).
- ICEpop CAPability measure for Adults (ICECAP-A; Al-Janabi et al., 2012) for the carer.
- Acceptance and Action Questionnaire II (AAQ-II; Bond et al., 2011).
- Motor Neuron Disease Behavioural Instrument (MiND-B), with additional FRS adapted questions

5.6 Withdrawal information

Where possible, the time and reason for withdrawal from the study will be ascertained and reported. Reasons may be grouped and frequencies reported by treatment group.

6.0 Analysis

6.1 Framework and levels of statistical significance

Statistical analyses will use a classical frequentist approach. Statistical significance will be set at the conventional two-sided 5% level. Confidence intervals will be of corresponding 95% size.

6.2 Outcomes

No primary efficacy outcome is defined and the main outcomes of interest will relate to trial feasibility.

6.2.1 Feasibility Outcomes

Feasibility outcomes will be collected to enable an estimation of key parameters to inform a future trial, and to provide preliminary information about the impact of the intervention. These are:

- Numbers of potentially eligible participants.
- Number of participants subsequently recruited into the study.
- Attrition rate and reason for withdrawals.
- Use of the MiNDToolkit by carers:
 - engagement with the platform: number of times assessed;
 - length of time spent logged in;
 - which modules have been repeated and frequency of replay.
- Use of the MiNDToolkit by HCPs:
 - frequency of use,
 - duration and time taken;
 - which modules have been repeated and frequency of replay.
- Completion of online outcome measures:
 - time to completion;
 - number of non-completed outcomes (i.e. 'abandoned' before completion)

6.2.2 Efficacy Outcomes

The following outcome efficacy variables, all related to the carer of the person with dementia, are collected within one month of the end of the intervention.

- Patient Health Questionnaire 9
- Generalized Anxiety Disorder Questionnaire 7
- Carer Experience Scale
- ICEpop CAPability measure for Adults

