#### 1.2 Study Objectives

- To test the feasibility of the MiNDToolkit online intervention in MND Specialist Settings;
- 2) To explore the potential of several outcome measures for future evaluation studies (trials)

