#### Screening measures

- Carer socio-demographic, medical history proforma.
- ALS-Functional Rating Scale Revised (ALSFRS-R; Cedarbaum et al., 1999) is an interview-based assessment of progression of functional disability in people with MND. Adapted for completion by carer.
- Motor Neurone Disease Behavioural Instrument (MiND-B; [name] et al., 2014) is a multiple domain carer-rated short form measure of changes in the behaviour of the

**person** with MND. For the purposes of this study, we will also ask carers to rate the distress caused by the behaviour.

The screening assessment will be automatically scored by the online platform. If the screening criteria are not met, the carer will be contacted again in approximately three months for a repeat screening assessment, when symptoms of the person with MND may have changed.

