#### Baseline measures

Outcome measures being tested:

- The Patient Health Questionnaire 9 (PHQ-9; Kroenke et al., 2003) is a very brief multipurpose self-rated instrument for screening, diagnosing, monitoring and measuring the severity of depression for the carer.
- The Generalized Anxiety Disorder Questionnaire 7 (GAD-7; Kroenke et al., 2007) is a very brief self-rated questionnaire measuring for symptoms of generalized anxiety disorder for the carer.
- The Adapted Client Service Receipt Inventory (CSRI; Beecham & Knapp, 2001) is a tool to collect information on the range of services and supports currently being utilised by the person with MND.
- The Carer Experience Scale (CES; Al-Janabi et al., 2008) is a short, self-report measure for the carer of their caring experience for use in economic evaluation that assesses care-related quality of life in multiple domains including activities outside caring, fulfilment from caring, and relationship with the care recipient.
- ICEpop CAPability measure for Adults (ICECAP-A; AI-Janabi et al., 2012) is the short measure of wellbeing for the carer. The ICECAP-A is a measure of capability of the general adult (18+) population for use in economic evaluation.
- Acceptance and Action Questionnaire II (AAQ-II; Bond et al., 2011) is a 7-item selfreport questionnaire assessing people's general levels of **psychological flexibility**, the ability to be open, present-focused, and to change or persist in behaviour according to changing internal and external circumstances.

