#### Post-intervention assessment (within 1 month after the end of the intervention)

After the three-month intervention or usual treatment period, participants will be notified of the post-intervention assessment to complete via the platform.

Participants will be asked to complete the same assessments to that of the screening/pre-intervention assessment minus the socio-demographic, medical history questionnaires. In summary, the post-intervention assessment will include the following:

- About the person with MND: ALSFRS-R, MiND-B; FRS adapted, CSRI
- Carer questionnaires: PHQ-9, GAD-7, CES, ICECAP-A, CSRI, AAQ-II (six outcome measures being tested)

If post-intervention assessments are not completed after one week of the notification, a reminder will be sent. After a further week, participants will be contacted by telephone and given the option to complete the questionnaires over the phone with a researcher.

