# 2. To preliminarily explore the impact of the MiNDToolkit intervention on relevant carer variables, such as wellbeing, distress, quality of life.

Data analyses: the data analyses will be used to assess: (i) the degree of completion of each outcome measure and (ii) potential impact of the intervention on each.

(i) We will provide an estimate of the number of individuals completing each outcome measure and provide a 95% confidence interval with each estimate. We will also assess the number of missing items and for each with attention to any particular pattern. The distribution of each measure will be inspected to assess the possibility of 'ceiling' or 'flooring' effects. which would make an outcome inappropriate for a trial.

(ii) A comparison will be made between the MiNDToolkit and treatment as usual group with respect to each of the above outcome measures. Assuming a Normal distribution (or after an appropriate transformation) the difference in means will be estimated with a 95% confidence interval. The difference will also be expressed as a 'generic' (or Cohen's) Effect Size in order to assess the relative impact on each measure. The within group standard deviation will also be estimated, with 95% confidence intervals, which will be useful for future studies.

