6.3 Analysis Methods

The primary set of analyses will be related to the feasibility information on participant ‘flow’ and outcome data availability to inform the design of a future trial. Numbers of eligible participants, recruitment, and attrition rates will be compared with those of published studies in MND interventions, to evaluate if the MiNDToolkit was well accepted by families and professionals, and feasible for professionals. Formally, we will estimate, where possible, each rate with an associated 95% confidence interval. Of note, current published studies may not provide the ideal estimates for comparison to our proposed study, given the differences in the nature of the intervention. For this reason, we will have a cautious approach in the interpretation of attrition rates for the MiNDToolkit.

The distribution of each measure will be inspected to assess the possibility of ‘ceiling’ or ‘flooring’ effects, which would make an outcome inappropriate for a trial. The standard deviation, for Normally distributed variables, will be estimated with 95% confidence intervals, for use in future sample size calculations.

In addition, initial estimates of efficacy will also be provided. These will be estimated as between-group differences from a general linear model with appropriate link function and error distribution. Each model will include the baseline value of the outcome variable at baseline where available.

A number of individuals continued to access the online toolkit post the main follow-up time point and complete questionnaires. These will also be summarized but not included in any estimate of efficacy.

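### SAP 6.2.2 leaves out AAQ-II and CSRI, two of the six outcome measures that the protocol undertakes to compare between groups, and gives no reason

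*SAP*

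**What the plan says.** The second study objective, worded alike in protocol 1.2 and SAP 2.2, is "To explore the potential of several outcome measures for future evaluation studies (trials").

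Protocol 2.5 gives the candidate measures twice. Under Baseline measures, six instruments follow the label "Outcome measures being tested". Under Post-intervention assessment they are repeated as the carer questionnaires: "PHQ-9, GAD-7, CES, ICECAP-A, CSRI, AAQ-II (six outcome measures being tested"). CSRI is also listed there among the items about the person with MND.

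Protocol 2.6, item 2, says that the analysis will assess ("i) the degree of completion of each outcome measure and (ii) potential impact of the intervention on each". For the second part it states: "A comparison will be made between the MiNDToolkit and treatment as usual group with respect to each of the above outcome measures". The planned outputs are a difference in means with a 95% confidence interval, a standardised effect size, and the within-group SD with its interval. For the first part it plans the number completing each measure, with a 95% confidence interval, and a check for floor and ceiling effects.

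SAP 6.2.2 introduces its list with "The following outcome efficacy variables, all related to the carer of the person with dementia" and names PHQ-9, GAD-7, CES and ICECAP-A. SAP 6.3 then plans between-group estimates from a model adjusted for the baseline value where there is one. SAP 5.5 includes AAQ-II and MiND-B among the baseline descriptives. The SAP does not mention CSRI.

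On MiND-B, protocol 2.5 (Screening measures) adds that "we will also ask carers to rate the distress caused by the behaviour". MiND-B is repeated post-intervention, but the SAP does not mention the distress rating.

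**The concern.** A SAP normally carries out the protocol's analysis commitments or explains where it departs from them. Here the list that feeds the efficacy model is shorter than the protocol's, and nothing in the SAP accounts for the difference. An analyst who follows the SAP as written would produce no post-intervention group comparison for AAQ-II or CSRI, although the protocol promises one and schedules the data for it.

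This matters more than it would for a minor secondary endpoint, because choosing among candidate outcome measures is one of the study's two objectives. No primary efficacy outcome is defined (SAP 6.2), so there is no hierarchy or error-control argument for estimating some candidates and not others. A future trial team would have a standardised difference for four candidates and a blank for two, with no way to tell whether the blank was a decision or an oversight. Readers who compare the protocol with the report would see two measures missing without explanation.

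**Working it through.** This is a comparison of lists, so the main check is a count.

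**The protocol's own figure.** The post-intervention list in protocol 2.5 is PHQ-9, GAD-7, CES, ICECAP-A, CSRI, AAQ-II. That is 6 instruments, which agrees with the six stated there and with the baseline list.

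**Set against the SAP.**

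| Measure | Protocol 2.5: under test | SAP 5.5: baseline summary | SAP 6.2.2: efficacy outcome |
|---|---|---|---|
| PHQ-9 | yes | yes | yes |
| GAD-7 | yes | yes | yes |
| CES | yes | yes | yes |
| ICECAP-A | yes | yes | yes |
| AAQ-II | yes | yes | no |
| CSRI | yes | no | no |

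- In the protocol but not in SAP 6.2.2: 6 − 4 = 2 (AAQ-II and CSRI), or 2/6 = 33% of the measures under test.
- In neither SAP list: 1 (CSRI).
- After the fix: 6 of 6.

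**Does another SAP section supply the comparison?** No. SAP 6.5 (Additional analyses) plans no subgroup or sensitivity analyses. The last paragraph of 6.3 concerns questionnaires completed after the main follow-up and keeps them out of any efficacy estimate.

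**Which outputs are missing, and which are only unclear?**

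- *Group comparison:* missing for AAQ-II and CSRI.
- *Distribution and SD:* SAP 6.3 refers to each measure without a list. It can be read as covering all six or only the four in 6.2.2.
- *Completion:* SAP 6.2.1 counts non-completed outcomes without naming them. SAP 6.4 gives one overall proportion who abandon online entry, with a 95% confidence interval. Protocol 2.6 asks for an estimate per measure. A pooled proportion cannot show which questionnaire is being left unfinished. This gap affects all six measures.

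**How precise would the missing comparisons be?** The SAP gives up to 30 carers and no allocation ratio. Assume 1:1 and no baseline adjustment. The 95% half-width for a standardised mean difference is t(0.975, 2n−2) × √(2/n):

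- n = 15 per arm: 2.048 × √(2/15) = 0.75 SD.
- n = 10 per arm: 2.101 × √(2/10) = 0.94 SD.

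The 95% interval for a pooled SD at 15 per arm (28 degrees of freedom) runs from √(28/χ²(0.975)) to √(28/χ²(0.025)), that is 0.79 to 1.35 times the estimate.

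Any effect estimate will be imprecise. That holds equally for the four retained measures, so it does not explain leaving out two.

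**The case against.** The strongest reply is that 6.2.2 is confined to outcomes about the carer, whereas protocol 2.5 describes CSRI as recording services used by the person with MND. That is a fair reason for CSRI to sit outside a carer efficacy list. It does not explain why no other SAP section names CSRI, and it does not help with AAQ-II, a self-report scale listed among the carer questionnaires.

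The second reply is that this is a feasibility study whose main analyses concern participant flow and data availability, with efficacy estimates as an addition. That lowers the stakes and stands to that extent. It does not remove the protocol's commitment to a comparison on each measure.

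Three stronger readings are tempting, and the documents do not support them:

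- *That objective 2 cannot be answered.* The objective is to explore several measures. It fixes no number and does not require an effect estimate. Completion and distribution carry much of it, and the protocol still prescribes the rest.
- *That AAQ-II and CSRI get no completion, distribution or SD output.* SAP 6.2.1, 6.3 and 6.4 are not limited to the four efficacy outcomes. The wording is unclear, but it does not exclude them.
- *That follow-up data influenced the choice of outcomes.* The SAP does use the past tense, for example "A number of individuals continued to access the online toolkit post the main follow-up time point and complete questionnaires", and 6.4 does so about late entry. These sentences show knowledge of how follow-up was running. They do not show that outcome values by arm had been seen.

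The distress rating is a weaker matter. It is an add-on to MiND-B, which the protocol treats as a screening measure and a trigger for modules, and it is not one of the six. The heading of protocol 2.6, item 2, gives distress as an example of a carer variable but does not tie the word to this rating.

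**Conclusion.** The mismatch is real and should be corrected. Two of six measures (AAQ-II and CSRI) have no planned post-intervention group comparison in the SAP, contrary to protocol 2.6, and no reason is given. AAQ-II is the clearer inconsistency within 6.2.2. CSRI is the clearer omission from the SAP as a whole.

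The 33% applies to the efficacy list only, not to every post-intervention output. A secondary gap is that per-measure completion with a confidence interval, promised in protocol 2.6, is not spelled out in the SAP for any measure. A lesser one is that the MiND-B distress rating has no stated analysis.

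The conclusion assumes that the outcome measures in the protocol 2.6 comparison are the six named in 2.5. This is the natural reading, since 2.5 labels them so in two places. The precision figures assume 1:1 allocation and are illustrative; the conclusion does not depend on them.

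**What to change.** 1. Add AAQ-II to SAP 6.2.2, analysed with the same baseline-adjusted model as the other four.
2. Add CSRI to the SAP as a service-use outcome, under its own heading if 6.2.2 is to stay limited to the carer, with completeness, distribution and summaries by arm. If the analysis stops short of the difference with interval in protocol 2.6, say so and why.
3. In SAP 6.3, state that the distribution and SD outputs cover all six measures by name, and that completion is reported for each with a 95% confidence interval.
4. If a measure is left out deliberately, give the reason and state whether outcome data had been viewed when that was decided.
5. As a secondary matter, say what will be done with the MiND-B distress rating. A descriptive summary by arm would be enough.
6. While editing 6.2.2, correct the description of the person cared for, which refers to dementia although the trial population is carers of people with MND.

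The cost is SAP wording and a few table rows. The protocol already schedules these measures post-intervention, so sample size and participant burden do not change.
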